10.2 FLOW CHART PHARMACOKINETIC ASSESSMENTS

BLOOD SAMPLING TIMES FOR PHARMACOKINETICS

| Course | Week | Visit | Day | Time point after dose (h:min) | CRF time | Sample number | BI 836909 analysis in serum | ADA** analysis |
|--------|------|-------|-----|------------------------------------|---------------|---------------|-----------------------------|----------------|
| 1 | 1 | 1 | 1 | Before start of infusion | 0:00 | S1-A | X | X |
| | | | | | 1:00 | S2-A | X | |
| | | | | | 2:00 | S3-A | X | |
| | | | | | 4:00 | S4-A | X | |
| | | | | | 8:00 | S5-A | X | |
| | | | 2 | | 24:00 | S6-A | X | |
| | | | 3 | | 48:00 | S7-A | X | |
| 1 | 1 | 2 | 8 | 168h after start of infusion | 168:00 | S8-A | X | |
| 1 | 2 | 3 | 15 | 336h after start of infusion | 336:00 | S9-A | X | X |
| 1 | 3 | 4 | 22 | 504 h after start of infusion | 504:00 | S10-A | X | |
| 1 | 4 | 5 | 29 | Before end of infusion in cycle 1* | 671:50 | S11-A | X | |
| | | | | | 673:00 | S12-A | X | |
| | | | | | 674:00 | S13-A | X | |
| | | | | | 676:00 | S14-A | X | |
| | | | | | 680:00 | S15-A | X | |
| | | | 30 | | 696:00 | S16-A | X | X |
| 2 | 1 | 1 | 1 | Before start of infusion | 0:00 | S17-A | | X |
| 2 | 2 | 3 | 15 | 14 days after start of infusion | 336:00 | S18-A | X | X |

Proprietary confidential information.

© 2018 Boehringer Ingelheim International GmbH or one or more of its affiliated companies. All rights reserved.

This document may not - in full or in part - be passed on, reproduced, published or otherwise used without prior written permission.

| Course | Week | Visit | Day | Time point after dose (h:min) | CRF time | Sample number | BI 836909 analysis in serum | ADA** analysis |
|--------|------|-------|-----|---------------------------------|----------|---------------|-----------------------------|----------------|
| 2 | 3 | 4 | 22 | 22 days after start of infusion | 504:00 | S19-A | X | |
| 2 | 4 | 5 | 29 | Before stop of infusion | 671:50* | S20-A | X | X |
| 3 | 1 | 1 | 1 | Before start of infusion | 0:00 | S21-A | | X |
| 3 | 2 | 3 | 15 | 14 days after start of infusion | 336:00 | S22-A | X | X |
| 3 | 3 | 4 | 22 | 22 days after start of infusion | 504 | S23-A | X | |
| 3 | 4 | 5 | 29 | Before stop of infusion | 672:00* | S24-A | X | X |
| 4 | 1 | 1 | 1 | Before start of infusion | 0:00 | S25-A | | X |
| 4 | 2 | 3 | 15 | 14 days after start of infusion | 336:00 | S26-A | X | X |
| 4 | 3 | 4 | 22 | 22 days after start of infusion | 504:00 | S27-A | X | |
| 4 | 4 | 5 | 29 | Before stop of infusion | 671:50* | S28-A | X | X |
| 5 | 1 | 1 | 1 | Before start of infusion | 0:00 | S29-A | | X |
| 5 | 2 | 3 | 15 | 14 days after start of infusion | 336:00 | S30-A | X | X |
| 5 | 3 | 4 | 22 | 22 days after start of infusion | 504:00 | S31-A | X | |
| 5 | 4 | 5 | 29 | Before stop of infusion | 671:50* | S32-A | X | X |

*10 minutes before stop of infusion

** Anti Drug Antibodies

Proprietary confidential information.

© 2018 Boehringer Ingelheim International GmbH or one or more of its affiliated companies. All rights reserved.

This document may not - in full or in part - be passed on, reproduced, published or otherwise used without prior written permission.

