[figure not shown]

[figure not shown]
[figure not shown]
[figure not shown]
[figure not shown]

Clinical Trial Protocol

Doc. No.: c02587386-05

| | |
|--|--|
| EudraCT No.: | 2014-004896-22 |
| BI Trial No.: | 1351.1 |
| BI Investigational Product(s): | BI 836909 |
| Title: | An open label, phase I, dose escalation study to characterize the safety, tolerability, pharmacokinetics, and pharmacodynamics of intravenous doses of BI 836909 in relapsed and/or refractory multiple myeloma patients |
| Clinical Phase: | Phase I |
| Clinical Trial Leader: |  Phone: +  Fax: +  |
| Co-ordinating Investigator: |  Phone: +  Fax: +  |
| Status: | Final Protocol (Revised Protocol (based on global amendment 4)) |
| Version and Date: | Version 5.0 Date: 26 Nov 2018 |
| Page 1 of 161 | |
| Proprietary confidential information. © 2018 Boehringer Ingelheim International GmbH or one or more of its affiliated companies. All rights reserved. This document may not - in full or in part - be passed on, reproduced, published or otherwise used without prior written permission. | |

CLINICAL TRIAL PROTOCOL SYNOPSIS

| | | | |
|--|--------------------------------|-------------------------------------|--------------------------------------|
| Name of company Boehringer Ingelheim | | Tabulated Trial Protocol | |
| Name of finished product: Not applicable | | | |
| Name of active ingredient: BI 836909 | | | |
| Protocol date: 10 Feb 2015 | Trial number: 1351.1 | | Revision date: 26 Nov 2018 |
| Title of trial: An open label, phase I, dose escalation study to characterize the safety, tolerability, pharmacokinetics, and pharmacodynamics of intravenous doses of BI 836909 in relapsed and/or refractory multiple myeloma patients | | | |
| Co-ordinating Investigator: [REDACTED] | | | |
| Trial site(s): Multi-centre | | | |
| Clinical phase: I | | | |
| Objective(s): 
Primary objective: To determine the maximum tolerated dose (MTD) as well as the dose limiting toxicities (DLT) of a 6-week regimen of BI 836909 given as continuous intravenous infusion in patients with relapsed and/or refractory multiple myeloma.
 
Secondary objectives:
 
 • Recommended dose for further development • To provide preliminary findings on the safety profile and assess pharmacokinetic profile of BI 836909 • To assess pharmacodynamic and anti-tumoral activity of BI 836909 • To evaluate immunogenicity of BI 836909 | | | |

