4. TREATMENTS

4.1 TREATMENTS TO BE ADMINISTERED

4.1.1 Identity of BI investigational product and comparator product(s)

Substance (INN): BI 836909

Pharmaceutical form: Powder for solution for infusion after dilution in water plus 5 ml bag-diluent

Source: Boehringer Ingelheim Pharma GmbH & Co. KG

Unit strength: 75 µg lyophilisate

Daily dose: See [Section 4.1.5](#)

Duration of use: BI 836909 will be administered as a continuous 4-week infusion followed by a 2-week break for 5 cycles or until progression, unacceptable adverse events or other reason necessitating withdrawal. In case of ongoing clinical benefit a maximum of 5 additional treatment cycles can be given if considered indicated by the treating investigator. This means that a maximum of 10 cycles can be given to a patient.

Route of administration: Intravenous infusion

Posology: Rate controlled infusion; the flow rate is set to 2.6 ml/h (250 ml in 96 hours).

Substance (INN): Bag Diluent for BI 836909

Pharmaceutical form: 5 ml diluent

Source: Boehringer Ingelheim Pharma GmbH & Co. KG

Unit strength: N.A.

Daily dose: N.A.

Duration of use: 5 ml bag diluent will be added to each bag independent of dose given and will be administered as a continuous 4-week infusion followed by a 2-week break for 5 cycles or until progression, unacceptable adverse events or other reason necessitating withdrawal.

Route of administration: Intravenous infusion

Proprietary confidential information.

© 2018 Boehringer Ingelheim International GmbH or one or more of its affiliated companies. All rights reserved.

This document may not - in full or in part - be passed on, reproduced, published or otherwise used without prior written permission.

Posology: Rate controlled infusion; the flow rate is set to 2.6 ml/h (250 ml in 96 hours).

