5.2 SAFETY

5.2.1 Endpoint(s) of safety

The primary objective is to assess the safety of the drug in humans and to determine the MTD of BI 836909.

Primary Endpoints are the following:

- Maximum tolerated dose (MTD) of BI 836909
MTD is defined as the highest dose level tested where ≤ 1 patient out of 6 develop dose limiting toxicity. If MTD cannot be determined based on safety findings, a recommended dose for further development will be determined based on pharmacokinetic and pharmacodynamic data.
The MTD will be defined on the basis of DLT observed during cycle 1. However, for those patients who receive more than one cycle of BI 836909, all adverse events corresponding to the definition of DLT ([Section 5.2.1.1](#)) will be considered for the purpose of confirming the MTD and for the selection of the recommended dose for further development. In regular intervals, all available safety data including adverse events qualifying for DLT will be reviewed by the safety committee.
- Number of patients with dose limiting toxicities

The safety of BI 836909 will be assessed by a descriptive analysis of incidence and intensity of adverse events graded according to CTCAE (version 4.03), the incidence dose limiting toxicity (DLT), laboratory data and results of physical examination.

Further endpoint of safety is

- Immunogenicity of BI 836909 (frequency of patients developing anti-drug antibodies)

The safety data will be reviewed in regular intervals as well as ad hoc if needed.

The safety endpoints will be assessed in a descriptive way without confirmatory analyses.

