6.2.5 Follow-Up Period

6.2.5.1 End of treatment visit (EOT)

The EOT visit will be performed after permanent discontinuation of trial medication for any reason as soon as possible but no later 1 week after permanent discontinuation of the trial medication or when the investigator decided with the patient to permanently discontinue the trial medication or became aware that the trial medication had been terminated.

Proprietary confidential information.

© 2018 Boehringer Ingelheim International GmbH or one or more of its affiliated companies. All rights reserved.

This document may not - in full or in part - be passed on, reproduced, published or otherwise used without prior written permission.

Table 6.2.5.1: 1 Visit at the End of Treatment (EOT)

| | |
|---|---|
| ECG (Section 5.2.5) | Resting 12-lead ECG (digital) |
| Physical examination (Section 5.2.6.2) | A general physical examination as well as an orientated neurological examination will be performed, preferably by the same investigator throughout the study to enable comparability. This includes blood pressure, heart rate and temperature |
| | |
| Weight (Section 5.2.6.2) | Weight is measured; preferably, the same weight scale should be used throughout the study to ensure consistency of data collected. |
| Safety laboratory (Section 5.2.4) | Haematology, biochemistry, coagulation parameters, and urinalysis (dipstick). |
| Disease assessment: clinical and blood/MRI (Section 5.5.1) | Clinical: if patient has any new clinical symptoms of multiple myeloma, these should be recorded in the “disease assessment” page and as an AE when applicable (see Section 5.2.2.1). |
| | |
| Bone Marrow aspirate (Section 5.6.1) | 
Total body MRA should be performed.
 
The following assessments will be performed:
 
 • MM cells in bone marrow; percentage (%) of plasma cells in bone marrow should be assessed locally according to institutional standards and documented in eCRF. • BCMA expression by myeloma cells in bone marrow • MRD (in case M protein/FLC becomes undetectable) 
Obtain bone marrow biopsy if aspirate could not be obtained (punctio sicca). One sample of bone marrow will be provided for DNA banking.
 |

Proprietary confidential information.

© 2018 Boehringer Ingelheim International GmbH or one or more of its affiliated companies. All rights reserved.

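### No anti-drug antibody sample is scheduled at EOT or in cycles 6-10, and in cycles 2-5 the last one is drawn on infusion, so the ADA frequency may be underestimated.

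*Protocol*

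**What the plan says.** The Protocol synopsis lists as a secondary objective "To evaluate immunogenicity of BI 836909". Section 5.2.1 turns this into an endpoint, "Immunogenicity of BI 836909 (frequency of patients developing anti-drug antibodies", and ranks it as a further endpoint of safety.

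Appendix 10.2 fixes the sampling. In cycle 1, ADA is drawn before the infusion, on day 15, and on day 30, which is 24 hours after the infusion ends. In each of cycles 2-5 it is drawn on day 1 before the infusion, on day 15, and on day 29. The day 29 rows carry a footnote that sets the time at "10 minutes before stop of infusion". For cycle 2 the row is "Before stop of infusion | 671:50* | S20-A | X | X", and for cycle 5, the last row of the table, it is "Before stop of infusion | 671:50* | S32-A | X | X". Sample numbers run from S1-A to S32-A without a gap, so the table itself looks complete.

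On treatment length, Section 4.1.1 states: "This means that a maximum of 10 cycles can be given to a patient". The EOT table in Section 6.2.5.1 includes safety blood ("Haematology, biochemistry, coagulation parameters, and urinalysis (dipstick") but shows no ADA sample. The REP table in Section 6.2.5.2 lists adverse events, patient status and other myeloma therapy, with no blood draw.

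**The concern.** The endpoint counts patients who develop antibodies. A patient counts only if a sample is taken at a time when antibodies are present and can be detected. Any stretch of time without a sample can lower the reported frequency but cannot raise it.

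Two stretches stand out. The first is cycles 6-10, where nothing is scheduled. The patients treated there are those with ongoing benefit and the longest exposure. The second is the end of treatment. From cycle 2 on, each off-infusion ADA sample is a pre-infusion sample on day 1, so it exists only if that cycle is started. The final cycle never has a following day 1, and its last sample is taken with drug still running.

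At stake is the completeness of an immunogenicity figure in a first-in-human trial. The dose-escalation rule and the MTD do not depend on it.

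**Working it through.** The plan gives no figure for ADA incidence, onset or assay performance, so there is none to reproduce. The check counts the ADA marks in Appendix 10.2 and places them on the study calendar.

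**Count of ADA marks**
- Cycle 1: 3 (pre-infusion, day 15, day 30). Cycles 2-5: 3 each. Total 3 + 4 × 3 = 15.
- Baseline: 1 (S1-A). Post-baseline: 15 − 1 = 14.
- On infusion: day 15 of cycles 1-5 (5) plus day 29 of cycles 2-5 (4) = 9.
- Off infusion, post-baseline: cycle 1 day 30 (1) plus day 1 of cycles 2-5 (4) = 5.

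The cycle 3 row reads "Before stop of infusion | 672:00* | S24-A | X | X". Its clock time is 10 minutes later than in the other cycles, yet it carries the same footnote. This small inconsistency should be tidied but does not change the count.

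**Timing.** A cycle lasts 42 days (4 weeks on, 2 weeks off). Study day = (cycle − 1) × 42 + day in cycle. Planned infusion ends on day 29 of the cycle. For example, cycle 5 day 29 is 4 × 42 + 29 = 197, and cycle 10 day 29 is 9 × 42 + 29 = 407.

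| Cycles received | Last ADA sample (study day) | Last off-infusion ADA sample | Planned end of infusion | Last ADA sample to end of infusion |
|---|---|---|---|---|
| 1 | 30 | 30 | 29 | sample is 1 day after the end |
| 2 | 71 | 43 | 71 | 10 minutes |
| 5 | 197 | 169 | 197 | 10 minutes |
| 6 | 197 | 169 | 239 | 239 − 197 = 42 days |
| 10 | 197 | 169 | 407 | 407 − 197 = 210 days |

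Cycles 3 and 4 follow the pattern of cycles 2 and 5. When the last cycle is 2-5, the last off-infusion sample lies 28 days before the planned end of infusion (for example 197 − 169). At 10 cycles, the infusion days in cycles without an ADA sample are 5 × 28 = 140 out of 10 × 28 = 280.

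**Back-up serum.** Section 5.5.2.2 allows leftover PK serum to be used for immunogenicity. From cycle 2 on, PK samples fall on days 15, 22 and 29, all during infusion, and none is scheduled after cycle 5 or at EOT. They do not fill either gap.

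**Size.** Let u be the share of patients developing ADA whose antibodies are never detectable in a scheduled sample. The reported frequency is then (1 − u) times the true one. The documents give no ADA rate, no onset time, no drug tolerance and no number of patients expected beyond cycle 5. No value or useful range for u follows from them.

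**The case against.** Several counter-arguments have force.

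- **The final cycle is sampled.** When the last cycle is 2-5, ADA is drawn in it on days 15 and 29. A reader might infer that antibodies from the last cycle cannot be seen. The documents do not support this: such antibodies are lost only if circulating drug masks them, and no drug-tolerance limit is given. For patients who continue, the day 1 samples also check the preceding cycle after the two-week break.
- **Early stoppers.** A reader might infer that a patient stopped in week 3 of cycle 1 is left with only the day 15 sample. Section 5.5 says that when an infusion is shortened, later PK and biomarker sampling times move with its actual end. ADA is a column of the PK chart, so on the natural reading the sample due 24 hours after infusion moves too.
- **Rank.** ADA frequency is a further endpoint in Section 5.2.1, all analyses are descriptive, and the escalation rule does not use it.
- **Blacked-out text.** Parts of Section 5.6, the biomarker flow chart, some EOT rows and the SAP's further-endpoint text cannot be read. An ADA draw at EOT cannot be wholly excluded, although Appendix 10.2 shows none.
- **Limits of an EOT sample.** EOT falls within 7 days of stopping, so it may be close to the end of infusion and too early for late antibodies.

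These points limit the claim but do not remove it. Even a fully drug-tolerant assay cannot find antibodies that first appear in cycles 6-10 or after the last sample.

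**Conclusion.** The point holds as a schedule gap with a possible downward bias. For cycles 6-10 and for time after the last sample, the loss follows from the calendar alone: between 42 days (6 cycles) and 210 days (10 cycles) from the last ADA sample to the planned end of infusion. For a final cycle 2-5, loss is possible only if circulating drug interferes with the assay. That is an assumption the documents neither confirm nor rule out.

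The size of the undercount is unknown, and any percentage attached to it would be invented. The conclusion also assumes that the blacked-out sections contain no ADA draw missing from Appendix 10.2. Given the endpoint's rank, the change is worth making because it is cheap and serves a stated objective. The MTD is not affected.

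**What to change.** - **Add an ADA row at EOT in Appendix 10.2 and in the EOT table of Section 6.2.5.1.** It should apply to all patients, including those treated in cycles 6-10 and those who stop early. Draw it with the EOT safety blood after the infusion has ended, preferably at least 24 hours after, as for S16-A in cycle 1.
- **Keep the day 29 ADA samples in cycles 2-5.** Dropping them to save tubes would remove a real observation for any patient who then misses EOT.
- **State the coverage when reporting.** Give the ADA frequency with a note that scheduled within-cycle sampling covers cycles 1-5 only, and with the number of patients who have an off-infusion sample after their last dose.
- **Correct the clock time of S24-A** or its footnote mark so that the two agree.

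The cost is one extra serum tube per patient at an existing blood draw. One sample at EOT still leaves cycles 6-10 without interim sampling, and antibodies arising after EOT would still be missed.

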10.3 DEFINITIONS OF LABORATORY AND CLINICAL TUMOR LYSIS SYNDROM

| Metabolic Abnormality | Criteria for Classification of Laboratory Tumor Lysis Syndrome | Criteria for Classification of Clinical Tumor Lysis Syndrome |
|----------------------------------|---|--|
| Hyperuricemia | Uric acid >8.0 mg/dl (475.8 μ mol/liter) in adults or above the upper limit of the normal range for age in children | |
| Hyperphosphatemia | Phosphorus >4.5 mg/dl (1.5 mmol/liter) in adults or >6.5 mg/dl (2.1 mmol/liter) in children | |
| Hyperkalemia | Potassium >6.0 mmol/liter | Cardiac dysrhythmia or sudden death probably or definitely caused by hyperkalemia |
| Hypocalcemia | Corrected calcium <7.0 mg/dl (1.75 mmol/liter) or ionized calcium <1.12 (0.3 mmol/liter) [†] | Cardiac dysrhythmia, sudden death, seizure, neuromuscular irritability (tetany, paresthesias, muscle twitching, carpopedal spasm, Trousseau's sign, Chvostek's sign, laryngospasm, or bronchospasm), hypotension, or heart failure probably or definitely caused by hypocalcemia |
| Acute kidney injury [‡] | Not applicable | Increase in the serum creatinine level of 0.3 mg/dl (26.5 μ mol/liter) (or a single value >1.5 times the upper limit of the age-appropriate normal range if no baseline creatinine measurement is available) or the presence of oliguria, defined as an average urine output of <0.5 ml/kg/hr for 6 hr |

*In laboratory tumor lysis syndrome, two or more metabolic abnormalities must be present during the same 24-hour period within 3 days before the start of therapy or up to 7 days afterward. Clinical tumor lysis syndrome requires the presence of laboratory tumor lysis syndrome plus an increased creatinine level, seizures, cardiac dysrhythmia, or death.

[†]The corrected calcium level in milligrams per deciliter = measured calcium level in milligrams per deciliter + 0.8 × (4 – albumin in grams per deciliter).

[‡]Acute kidney injury is defined as an increase in the creatinine level of at least 0.3 mg per deciliter (26.5 μ mol per liter) or a period of oliguria lasting 6 hours or more. By definition, if acute kidney injury is present, the patient has clinical tumor lysis syndrome.

Proprietary confidential information.

© 2018 Boehringer Ingelheim International GmbH or one or more of its affiliated companies. All rights reserved.

This document may not - in full or in part - be passed on, reproduced, published or otherwise used without prior written permission.

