5.2.1.1 Dose limiting toxicity

Dose limiting toxicity (DLT) is defined as any drug-related non-haematological adverse event CTCAE version 4.03 grade 3 or higher. The following grade 3 events will not be considered

Proprietary confidential information.

© 2018 Boehringer Ingelheim International GmbH or one or more of its affiliated companies. All rights reserved.

This document may not - in full or in part - be passed on, reproduced, published or otherwise used without prior written permission.

DLT: febrile neutropenia and infection responding to antibiotic/anti-infective treatment within 48 hours, fatigue, headache, insomnia, fever, hypotension.

Laboratory parameters of grade ≥ 3 but not considered clinically relevant and/or responding to routine medical management, will not be considered dose limiting toxicities.

Additional events that are considered DLT include:

- Persistent grade 4 neutropenia or thrombocytopenia until day 56 in the absence of detectable Multiple Myeloma as it may reflect a marrow toxic effect of BI 836909.

If infusion related reactions (IRR) or cytokine release syndromes (CRS) \geq grade 2 occur or constitute DLT events the safety committee may decide to switch to step dosing for the respective and any higher dose cohort. In that case the infusion will be started at 10(-30)% of the target dose on day 1 of the course and will be escalated to the full target dose from day 9 of course 1 on for the remainder of the course. Patients will be hospitalized and pre-medicated for the dose increase the same way they are for start of treatment. Once the safety committee decides to switch to step dosing patients that may have developed DLT due to IRR or CRS events may be replaced at the respective cohort by additional patients who will receive treatment with the adapted administration schedule (step dosing).

Although hematological adverse events (e.g. anemia, thrombocytopenia, neutropenia, lymphopenia) will not be considered DLT, complications resulting from hematological events, e.g. bleeding due to thrombocytopenia or grade 4 infection due to neutropenia are classified as non-hematological adverse events and are covered by the above definition of DLT. Nevertheless, hematological adverse events will be considered for definition of the dose for further development.

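### With the optional day 9 step-dosing scheme, the laboratory TLS window closes 24 hours before the increase to full dose, so TLS without acute kidney injury whose laboratory changes first appear after the step falls outside the trial definition

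*Protocol*

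**What the plan says.** Protocol 4.1.4.1.3 notes that CTCAE 4.03 does not clearly define when TLS is present. It therefore adopts the Cairo-Bishop classification for this trial, with presence meaning clinical TLS, and refers to Appendix 10.3.

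The footnotes to the Appendix 10.3 table set the conditions:
- Laboratory TLS needs two or more metabolic abnormalities "during the same 24-hour period within 3 days before the start of therapy or up to 7 days afterward".
- The clinical form builds on the laboratory form: "Clinical tumor lysis syndrome requires the presence of laboratory tumor lysis syndrome plus an increased creatinine level, seizures, cardiac dysrhythmia, or death".
- "By definition, if acute kidney injury is present, the patient has clinical tumor lysis syndrome". No time window is attached to this sentence.

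Protocol 5.2.1.1 lets the safety committee switch to step dosing after infusion-related reactions or cytokine release syndrome. The infusion starts at 10-30% of target and "will be escalated to the full target dose from day 9 of course 1 on for the remainder of the course". At that increase, "Patients will be hospitalized and pre-medicated for the dose increase the same way they are for start of treatment". Section 4.1.4.5 describes the same day 9 step for later cycles and possibly for new patients. Section 3.1.1 gives a different scheme: four days at the previous dose level, then the current one.

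Protocol 5.2.4.2 requires the TLS panel every 4-8 hours for the first 48 hours of course 1 and the first 24 hours of course 2. Flow chart footnote 12 ties the in-hospital safety laboratories to days 1-3 of cycle 1 and days 1-2 of cycle 2.

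**The concern.** The window suits a regimen whose full exposure starts on day 1. Under the day 9 scheme the patient spends the whole window on a fraction of the target dose, and the large rise in exposure comes after it has closed. No text in the protocol or SAP restarts the window at a dose increase or defines the start of therapy for step-dosed patients.

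The label matters because, under 4.1.4.1.3, TLS that is present is at least grade 3. If drug-related, it then meets the general DLT rule in 5.2.1.1, and TLS is also a listed AESI. Without the label, each component is judged separately. Laboratory values of grade 3 or higher that respond to routine management are not DLTs, and a low-grade dysrhythmia is not one either. Under the 3+3 rules in Protocol 3.2, one DLT in three patients expands a cohort and two in up to six exceed the MTD, so the status of one case can matter.

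The second issue is detection. If no panel is tied to the step-up, early laboratory changes after it may be found late.

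**Working it through.** This is date arithmetic; no power or error rate is involved.

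**Inputs**
- Window: up to 7 days after the start of therapy (Appendix 10.3).
- Day numbering: day of first administration is day 1, with no day 0 (SAP 6.7), so day *d* at the same clock time is (*d* − 1) × 24 h. The pharmacokinetic chart (Appendix 10.2) agrees: it puts day 8 at "168h after start of infusion" and day 15 at 336 h.
- Step to full dose: day 9, from 10-30% of target (5.2.1.1, 4.1.4.5).
- Infusion length: 4 weeks = 672 h.
- Visit window: ±3 days (flow chart, 6.1).

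**Window against step**
- Window closes: 7 × 24 = 168 h, day 8.
- Step: (9 − 1) × 24 = 192 h, which is also two 96 h bags.
- Gap: 192 − 168 = 24 h. If day 1 were counted as the first of the seven days, the window would close on day 7 and the gap would be two days.
- Full-dose time: 672 − 192 = 480 h = 20 days, of which 0 lie inside the window.
- Size of step: 100/30 = 3.3-fold to 100/10 = 10-fold.

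The 4-day scheme in 3.1.1 steps up at 96 h, day 5, with 168 − 96 = 72 h of the window left. The gap belongs only to the day 9 scheme.

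**Laboratory sampling**
- Panel at the start of course 1: 48/8 = 6 to 48/4 = 12 sampling times.
- Panel at the start of course 2: 24/8 = 3 to 24/4 = 6.
- Panel required at the step-up: none. The course 1 panel ends 192 − 48 = 144 h before it.
- Next scheduled chemistry after the step: nominally day 15, so 15 − 9 = 6 days. If the day 8 visit took place on days 5-8, the delay is 12 − 9 = 3 to 18 − 9 = 9 days. If that visit slips to days 9-11, the delay is 0 to 2 days.

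**What fails the definition, and what does not**
- Laboratory abnormalities present together by day 8, clinical event after day 9: meets the definition, because the window applies only to the laboratory abnormalities.
- Acute kidney injury at any time: meets it under its own footnote.
- No acute kidney injury, and qualifying laboratory abnormalities first appearing after the step: does not meet it.

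**The case against.** The strongest reply is that almost nothing is lost. The day 9 scheme is used only if the safety committee chooses it. Acute kidney injury still qualifies, CNS events of grade 2 or higher (such as seizures) are AESIs in their own right, and drug-related non-haematological events of grade 3 or higher are mostly DLTs under their own terms. The AESI list in 5.2.2.1 names TLS without citing Appendix 10.3, and SAP 7.8.1 applies no TLS window. A case therefore leaves the TLS count only if the investigator withholds the label because of the appendix. The safety committee also reviews all available safety data before each escalation (3.1.1). All of this stands, and it keeps the point minor.

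Some examples are weaker than they look. The appendix table includes "hypotension, or heart failure probably or definitely caused by hypocalcemia", and grade 3 hypotension is on the list of events exempt from DLT ("DLT: febrile neutropenia and infection responding to antibiotic/anti-infective treatment within 48 hours, fatigue, headache, insomnia, fever, hypotension"). But the footnote's shorter list omits hypotension, so its status is unclear even inside the window. Laboratory changes with a low-grade dysrhythmia are a cleaner example.

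One could also take the start of therapy to mean the start of full dose, which would remove the gap. No text says so, and the plain sense is the first infusion or the course start.

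On monitoring, a reader might infer that patients go unwatched at the step-up. The documents do not support that. They are hospitalised, 5.2.6.1 calls for continuous cardiac monitoring and repeated vital signs during hospitalisation for administration, and 4.1.4.1.3 requires TLS monitoring of all patients. What is missing is a fixed laboratory schedule.

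**Conclusion.** The concern holds in a limited form and is minor. Under the day 9 scheme the laboratory TLS window closes 24 hours before a 3.3- to 10-fold dose increase. TLS without acute kidney injury whose qualifying laboratory abnormalities first appear after that increase is then not TLS by the trial's own rule. The 4- to 8-hourly panel is not required at that point.

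A reader might infer that all clinical TLS after the step is excluded, or that such events go unreported. Neither follows: a patient with laboratory TLS by day 8 still qualifies, and the events remain reportable as adverse events. The cases actually misclassified are those made up of low-grade or DLT-exempt components, where the investigator applies the appendix literally.

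The conclusion assumes that the committee adopts the day 9 scheme, that the step occurs at about 192 h, and that therapy starts with the first infusion or the course start. The two footnotes also treat raised creatinine differently, but that is a separate wording matter unrelated to step dosing.

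**What to change.** - **Appendix 10.3:** add one sentence stating that for step-dosed patients the 7-day window also runs from the increase to full dose.
- **Section 5.2.4.2:** add one sentence requiring the same TLS panel every 4-8 hours for the first 48 hours after the step-up.

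The window need not be restarted at every course start or after every interruption to close this gap.

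The cost is about 6 to 12 local sampling times per step-up. That count includes any full safety laboratories taken in the same 48 hours, and the patients are already in hospital. The other downside is a slight departure from the published classification.
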